8.1.4 Post Injection Assessments in the Study Eye

Within 5 minutes after the injection, check vision for count fingers or hand motion.

• Tonometry (between 30 and 50 minutes after injection):

If the IOP is >30 mmHg or has increased by ≥ 10 mmHg from pre-injection, the IOP will be measured again at 60–80 minutes post-injection. If there are no safety concerns, the participant will be permitted to leave the clinic. If the IOP value is of concern to the Investigator, the participant will remain in the clinic and will be managed in accordance with the Investigator's clinical judgment. The latest post-injection IOP measured (prior to any intervention for increased IOP, if applicable) will be recorded on the post-treatment IOP eCRF.

The method of post-injection IOP measurement (such as Goldmann tonometry or Tonopen) must be the same as the pre-injection method and remain the same throughout the study for each participant.

8.1.5 Best Corrected Visual Acuity

Best corrected visual acuity (BCVA) will be measured utilizing the ETDRS method by certified, masked personnel at the study sites. The measurement should be performed following refraction, and prior to any examination requiring contact with the eye and prior to dilating the eyes. A BCVA Testing Procedure Manual and training materials will be provided to all sites by the third-party VA Examiner certification vendor.

8.1.6 Fundus Photography

Fundus photography (FP) will be performed at the study sites by certified, masked personnel. Where wide-field devices qualified by the Reading Center are available, wide-field FP should be performed. It is mandatory that the same model of device is used for the entire duration of the study.

Additional specifications and instructions regarding acceptable equipment and imaging techniques will be provided by the Reading Center.

8.1.7 Spectral Domain Optical Coherence Tomography

Spectral domain optical coherence tomography (SD-OCT) will be performed at the study sites by certified, masked personnel on a qualified instrument. It is mandatory that the same model of device is used for the entire duration of the study.

Additional specifications and instructions regarding acceptable equipment and imaging techniques will be provided by the Reading Center.

8.1.8 Fluorescein Angiography

Fluorescein angiography (FA) will be performed at all the study sites by certified, masked personnel. Where wide-field devices qualified by the Reading Center are available, wide-field FA should be performed. It is mandatory that the same model of device is used for the entire duration of the study.

Additional specifications and instructions regarding acceptable equipment imaging and imaging techniques will be provided by the Reading Center.

8.2 Safety Assessments

Planned time points for all safety assessments are provided in the SoA (Section 1.3).

8.2.1 Vital Signs

The following vital signs will be assessed with the participant in a seated position after resting for 5 minutes: blood pressure, pulse rate, and body temperature. Height and weight will be recorded at the screening visit only.

8.2.2 Clinical Safety Laboratory Assessments

See Appendix 2 for the list of clinical laboratory tests to be performed and refer to the SoA (Section 1.3) for the timing and frequency.

The Investigator or designee must review the laboratory report, document this review, and record any clinically significant changes occurring during the study as an AE. The laboratory reports must be filed with the source documents.

Abnormal laboratory findings associated with the underlying disease are not considered clinically significant unless judged by the Investigator to be more severe than expected for the participant's condition.

All laboratory tests with values considered clinically significantly abnormal during participation in the study or within 30 days after the last dose of study intervention should be repeated until the values return to normal or baseline or are no longer considered clinically significant by the Investigator or medical monitor.

- If clinically significant values do not return to normal/baseline within a period of time judged reasonable by the Investigator, the etiology should be identified, and the Sponsor notified.
- All protocol-required laboratory tests, as defined in Appendix 2, must be conducted in accordance with the SoA (Section 1.3).
- If laboratory values from non-protocol specified laboratory tests performed at the institution's local laboratory require a change in participant management or are considered clinically significant by the Investigator (e.g., SAE or AE or dose modification), then the results must be recorded.

8.2.3 Pregnancy Testing

Participant samples for pregnancy testing will be taken starting at the Screening visit and then at each visit through the end of the study in women of childbearing potential only as specified in the SoA (Section 1.3). Prior to enrollment in the study, female participants of childbearing potential and male participants must be advised of the importance of avoiding pregnancy or partner pregnancy, respectively, during the trial and the potential risks associated with an

unintentional pregnancy. Contraceptive and barrier guidance and collection of pregnancy information is described in Appendix 6.

8.3 Adverse Events, Serious Adverse Events, and Other Safety Reporting

The definitions of AEs and SAEs are provided in Appendix 3.

AEs will be reported by the participant (or, when appropriate, by a caregiver, surrogate, or the participant's legally authorized representative).

The Investigator and any qualified designees are responsible for detecting, documenting, and recording events that meet the definition of an AE or SAE and remain responsible for following up AEs that are serious, considered related to the study intervention or study procedures, or that caused the participant to discontinue the study (Section 7.0).

The method of recording, evaluating, and assessing causality of AEs and SAEs and the procedures for completing and transmitting SAE reports are provided in Appendix 3.

8.3.1 Time Period and Frequency for Collecting Adverse Event and Serious Adverse Event Information

After informed consent has been obtained but prior to initiation of study intervention, only SAEs caused by a protocol-mandated assessment should be reported. After initiation of study intervention (Day 1), all AE and SAE information will be collected until the final safety follow-up visit at Week 100 or the ET visit, if applicable.

All SAEs will be recorded and reported to the Sponsor or designee immediately and under no circumstance should this exceed 24 hours, as indicated in Appendix 3. The Investigator will submit any updated SAE data to the Sponsor within 24 hours of it being available.

Investigators are not obligated to actively seek information on AEs or SAEs after conclusion of the study participation. However, if the Investigator learns of any SAE, including a death, at any time after a participant has been discharged from the study, and he/she considers the event to be reasonably related to the study intervention or study participation, the Investigator must promptly notify the Sponsor.

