1.3 Schedule of Activities (SoA)

1.3.1 SoA-A

The following schedule of activities, SoA-A, shall be followed for all visits unless a participant is diagnosed with sight-threatening complication(s) of DR, as defined in Table 3 (Section 4.1.3.1), in their Study Eye. Upon diagnosis of sight-threatening complication(s) of DR in their Study Eye, participants shall then follow SoA-B (Section 1.3.2) instead of SoA-A.

Visit	Screening	Day 1	Week 8	Week 20	Week 32	Week 44	Week 48	Week 56	Week 68	Week 80	Week 92	Week 96/ET	Week 100 ¹²
Visit Windows (Days)	D-21 to D-1		+/-7	+/-14	+/-14	+/-14	+/-7	+/-14	+/-14	+/-14	+/-14	+/-7	+/-7
Informed Consent	Х												
Demographics	Х												
Medical & Ocular History	Х												
Inclusion/Exclusion Criteria Review	Х	Х											
Concomitant Medication Review ¹	Х	Х	Х	Х	Х	Х	Х	Х	Х	Х	Х	Х	Х
AE/SAE Review ²		Х	Х	Х	Х	Х	Х	Х	Х	Х	Х	Х	Х
General Assessments													
Vital Signs ³	Х	Х		Х			Х		Х			Х	
Laboratory ⁴	Х						Х					Х	
Plasma ADA/NAB Samples (pre-injection)		Х	Х		Х		Х		Х			Х	
Plasma PK/Biomarker Samples (pre-injection)		Х	Х		Х		Х		Х			Х	
Pregnancy Test ⁵ (WOCBP only)	Х	Х	Х	Х	Х	Х	Х	Х	Х	Х	Х	Х	Х
Ophthalmic Assessments ⁶													
BCVA ETDRS (4 meters) ⁷	Х	Х	Х	Х	Х	Х	Х	Х	Х	Х	Х	Х	
Ophthalmic Exam (Slit lamp, IOP ⁸ , dilated indirect ophthalmoscopy)	X	Х	Х	Х	Х	Х	Х	Х	Х	Х	Х	Х	
SD-OCT ⁹	Х		Х	Х	Х	Х	Х	Х	Х	Х	Х	Х	
Fundus Photos ⁹	Х		Х	Х	Х	Х	Х	Х	Х	Х	Х	Х	
Fluorescein Angiogram ⁹	Х			Х			Х		Х			Х	
Randomized study treatment (KSI-301 or sham) per IRT Designation ¹⁰		Х	Х	Х		Х			Х		Х		
Post-injection Assessments (vision check, IOP ⁸) ¹¹		Х	Х	Х		Х			Х		Х		

- Abbreviations: ADA = anti-drug antibody; AE = adverse event; BCVA = best corrected visual acuity; ET=Early Termination; ETDRS = early treatment diabetic retinopathy study; IOP = intraocular pressure; NAB = neutralizing antibody; PK = pharmacokinetics; SAE = serious adverse event; SD-OCT = spectral domain optical coherence tomography; WOCBP = women of childbearing potential.
- ¹ Record any concomitant medication used by the participant within 30 days prior to Day 1. Procedural medications administered (e.g., dilating drops, fluorescein) will not be recorded.
- ² After informed consent has been obtained but prior to initiation of study intervention, only SAEs caused by a protocol-mandated assessment should be reported. After initiation of study intervention (Day 1), all AEs will be reported until the final study visit or the ET visit if applicable. See Section 8.3.1.

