4.1.3 Administration of Study Intervention

All participants will be treated starting on Day 1 through Week 92 according to their respective treatment group. The IRT will determine the dosing schedule and adjust it in consideration of missed visits, out of window visits, and missing data during a visit. If a visit is missed at which study treatment is scheduled to be administered, the missed dose should be made up as close to the originally scheduled visit as possible using an unscheduled visit. Adjustments to study intervention due to development of sight-threatening complications of DR are described in Section 4.1.3.1.

As shown in the dosing regimen schematic provided in Figure 1, participants will be treated according to the group to which they were randomized, as follows:

• Group A - KSI-301 5 mg via Intravitreal Injection:

Intravitreal KSI-301 5 mg injection will be administered on Day 1, Week 8, Week 20, Week 44, Week 68, and Week 92.

• Group B - Sham Injection:

To preserve study masking, sham injections are administered to Group B participants at visits in which KSI-301 is administered to Group A participants. Thus, sham injections will be administered on Day 1, Week 8, Week 20, Week 44, Week 68, and Week 92.

For all study participants, non-treatment study visits will occur on Week 32, Week 48, Week 56, Week 80, and Week 96. A final safety assessment will occur on Week 100 and will be done via telephone call for all participants, except in WOCBP, in which case a site visit is required to administer a pregnancy test.

		Year 1								PE				
Week		0	(4)	8	(12)	(16)	20	(24)	(28)	32	(36)	(40)	44	48
KSI-301 5 mg	Q24W													
Sham		0		0			0						0	
						Ĩ	Year 2						SE	SA
Week		(52)	56	(60)	(64)	68	(72)	(76)	80	(84)	(88)	92	96	100 ª
KSI-301 5 mg	Q24W													
Sham						0						0		

Figure 1: Protocol KS301P106: Masked Dosing Regimens by Week

Abbreviations: PE = primary endpoint; Q24W = once every 24 weeks; SA = safety assessment; SE = secondary endpoint.

^a Week 100 is a final safety assessment that will be done via telephone call for all participants, except in WOCBP, in which case a site visit is required for the safety assessment that includes a pregnancy test.

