4.2.4 Choice of Duration of Treatment and Follow-up

The duration of treatment in this study will be approximately 92 weeks. The primary endpoint will be assessed at Week 48; secondary endpoints for efficacy will be assessed at Week 48, Week 96, and over time. These endpoints and associated duration of treatment were selected based on precedent for Phase 3 trials in NPDR (Lim 2020).

The choice of a safety follow-up interval of 8 weeks after the last dose is based on the expected duration of effect for KSI-301.

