5.1.2 General Inclusion Criteria

- 3. Male or female ≥ 18 years of age.
- 4. Capable of giving signed informed consent, as described in Appendix 1, which includes compliance with the protocols and restrictions listed in the informed consent form (ICF) and in this protocol.

- 5. Type 1 or 2 diabetes mellitus and HbA1c of $\leq 12\%$.
- 6. For women of childbearing potential: agreement to remain as abstinent (refrain from heterosexual intercourse) or use contraceptive methods that result in a failure rate of <1% per year during the treatment period and for at least 90 days after the last dose of study intervention.
 - A woman is considered of childbearing potential if she is post-menarchal, has not reached a post-menopausal state (≥12 months of amenorrhea with no identified cause other than menopause), and has not undergone surgical sterilization (removal of ovaries and/or uterus). The definition of childbearing potential may be adapted for alignment with local guidelines or requirements.
 - b. Examples of contraceptive methods with a failure rate of <1% per year include bilateral tubal ligation, male sterilization, established, proper use of hormonal contraceptives that inhibit ovulation, hormone-releasing intrauterine devices and copper intrauterine devices.
 - c. Contraception methods that do not result in a failure rate of <1% per year such as cap, diaphragm, or sponge with spermicide, or male or female condom with or without spermicide, are not acceptable.
 - d. The reliability of sexual abstinence should be evaluated in relation to the duration of the clinical trial and the preferred and usual lifestyle of the participant. Periodic abstinence (e.g., calendar, ovulation, symptothermal, or post-ovulation methods) and withdrawal are not acceptable methods of contraception.
- 7. For men: agreement to remain abstinent or use contraceptive measures and agreement to refrain from donating sperm, as defined below:
 - a. With female partners of childbearing potential, men must remain abstinent or use a condom plus an additional contraceptive method that together result in a failure rate of <1% per year during the treatment period and for at least

after the last dose of study intervention. Men must refrain from donating sperm during this same time period.

8. Ability and willingness to undertake all the scheduled visits and assessments.

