7.2 Participant Discontinuation/Withdrawal from the Study

Participants should be strongly encouraged to stay in the study and undergo as many scheduled visits as possible, with emphasis on the Weeks 48, 96, and 100 safety assessments. However, participants are free to withdraw from the study or study treatment at any time upon request. Participant participation in the study may be stopped at any time at the discretion of the Investigator or at the request of the Sponsor.

Participants who discontinue study treatment or active participation in the study will no longer receive study intervention. When a participant discontinues from study treatment or active participation in the study, the reason(s) for study treatment discontinuation or withdrawal shall be recorded by the Investigator or designee on the relevant page of the eCRF. Whenever possible, all participants who discontinue study treatment or withdraw from the study prematurely will undergo an ET visit. Participants who fail to return for final assessments must be contacted by the site by phone and in writing to obtain follow-up.

If a participant exits early from the study between visits, the Investigator or designee must attempt to contact the participant and advise the participant to return for a final visit to complete the exit procedures. If the participant is unable or unwilling to return for the Early Termination visit, the 'date of exit' will be the date that the participant was last seen at the site or contacted by other communication.

If the participant withdraws consent for disclosure of future information, the sponsor may retain and continue to use any data collected before such a withdrawal of consent.

If a participant withdraws from the study, he/she may request destruction of any samples taken and not tested, and the Investigator must document this in the site study records.

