8.3.5 Pregnancy

During the study, female and male participants are to be instructed to contact the Investigator immediately if they suspect they might be pregnant or if their partner becomes pregnant, respectively, and details will be collected. Additional urine or serum pregnancy testing may be performed during the study at the discretion of the Investigator, or in accordance with local requirements or regulations.

Pregnancy is not regarded as an AE unless there is a suspicion that an investigational product may have interfered with the effectiveness of a contraceptive medication. Any pregnancy that occurs during study participation must be reported using the same procedures as an SAE on a Sponsor prepared form. To ensure participant safety, each pregnancy must be reported to the Sponsor or its designee immediately (within 24 hours) after learning of its occurrence. The pregnancy must be followed up to determine outcome (including spontaneous miscarriage, elective termination, normal birth, or congenital abnormality) and status of mother and child, even if the participant was discontinued from the study. Pregnancy complications and elective terminations for medical reasons must be reported as an AE or SAE. Spontaneous miscarriages must be reported as an SAE.

Any SAE occurring in association with a pregnancy, brought to the Investigator's attention after the participant has completed the study, and considered by the Investigator as possibly related to the study treatment, must be promptly reported to the Sponsor.

Pregnancy is considered a criterion for discontinuation from the study; refer to Section 7.1 for additional information. Contraceptive and barrier guidance and collection of pregnancy information is described in Appendix 6.

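### For a participant who leaves early, AE and SAE collection ends at the ET visit however soon that follows the last dose, so it can fall well short of the protocol's own 8 weeks

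*Protocol*

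**What the plan says.** Protocol 4.2.4 gives both the interval and its reason: "The choice of a safety follow-up interval of 8 weeks after the last dose is based on the expected duration of effect for KSI-301".

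Protocol 8.3.1 defines the collection period by visit: "all AE and SAE information will be collected until the final safety follow-up visit at Week 100 or the ET visit, if applicable". Footnote 2 of SoA-A repeats the rule: "all AEs will be reported until the final study visit or the ET visit if applicable". The AE/SAE review row of SoA-B carries no footnote. In both schedules ET shares a column with Week 96, and the Week 100 AE review comes after it.

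Protocol 7.2 says that, whenever possible, "all participants who discontinue study treatment or withdraw from the study prematurely will undergo an ET visit". It sets no minimum time since the last dose. If a participant who exits between visits does not return for the ET visit, exit is dated when the participant was last seen at the site or otherwise contacted. Section 7.1 separately asks for an end-of-treatment visit 28 +/- 7 days after treatment is discontinued, or before a new regimen begins. It also says that stopping treatment is not withdrawal from the study.

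Once participation has ended, 8.3.1 does not oblige investigators to look for events. They report an SAE only if they learn of it and consider it reasonably related.

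SAP 8.2 counts an AE as treatment-emergent up to 28 days after the last dose. The period ends sooner if non-study anti-VEGF treatment or open-label KSI-301 starts in the study eye.

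On pregnancy, Protocol 5.1.2 requires women of childbearing potential to use contraception "for at least 90 days after the last dose of study intervention", while 8.3.5 says: "Any pregnancy that occurs during study participation must be reported using the same procedures as an SAE".

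**The concern.** Section 4.2.4 counts from the last dose; 8.3.1 counts to a visit. The two agree for a participant who completes the masked schedule on nominal dates. They need not agree for one who leaves early, because nothing ties the ET visit to the last injection. An early leaver also misses the Week 100 review that completers have after the visit sharing the ET column.

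At stake are new events in the weeks when, on the protocol's own reasoning, the drug is still expected to act. A participant may leave because something is already going wrong in the study eye, and for such a participant the weeks after the last injection matter most.

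**Working it through.** **Inputs.** Last masked dose at Week 92 (Protocol 4.1.3: "Intravitreal KSI-301 5 mg injection will be administered on Day 1, Week 8, Week 20, Week 44, Week 68, and Week 92"). Windows from SoA-A: Week 92 +/- 14 days, Week 100 +/- 7 days. Stated interval of 8 weeks (4.2.4). End-of-treatment visit at 28 +/- 7 days (7.1). Treatment-emergent window of last dose + 28 days (SAP 8.2). Contraception for at least 90 days (5.1.2).

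**1. The protocol's own figure.** (100 - 92) x 7 = 56 days, which is the stated 8 weeks. It reproduces on nominal dates.

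**2. Early leavers.** Days of collection = date of ET (or exit) minus date of last dose. The protocol gives this no lower bound.

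| Situation | Days collected | Short of 56 | Short of 28 |
|---|---|---|---|
| Exit dated at the dosing visit, no ET visit | 0 | 56 | 28 |
| ET one week after dosing | 7 | 49 | 21 |
| ET at the 7.1 visit, earliest (28 - 7) | 21 | 35 | 7 |
| ET at the 7.1 visit, nominal | 28 | 28 | 0 |
| ET at the 7.1 visit, latest (28 + 7) | 35 | 21 | 0 |

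The last three rows assume that the ET visit is the 7.1 visit and that discontinuation is dated at the last dose. If the decision comes later in a dosing interval, the gap from the last dose is longer. The first row assumes that the telephone and written contact required by 7.2 does not reach the participant.

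**3. Completers.** Week 92 is day 644 and Week 100 is day 700.
- Shortest: (700 - 7) - (644 + 14) = 693 - 658 = 35 days.
- Longest: (700 + 7) - (644 - 14) = 707 - 630 = 77 days.

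The range is symmetric about 56.

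**4. Share of the schedule exposed.** With masked doses at Weeks 0, 8, 20, 44, 68 and 92, the time before Week 92 that lies within 8 weeks of a dose is 8 + 8 + 8 + 8 + 8 = 40 weeks, and 40/92 = 43%. If withdrawals were spread evenly over those 92 weeks (an assumption), somewhat under half of leavers would go within 56 days of a dose.

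**5. Pregnancy.** For an on-time completer dosed at Week 92, 90 - 56 = 34 days of required contraception fall after participation ends. Within the visit windows the figure runs from 90 - 77 = 13 to 90 - 35 = 55 days.

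**The case against.** **Existing events are followed.** Section 7.1 follows an AE that led to discontinuation to resolution or until no further improvement is expected, over at least 3 months. Section 8.3.3 follows all SAEs and AEs of special interest. This stands, and it covers much of what happens to someone who leaves because of an ocular event. It does not cover an event that starts after the ET visit.

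**Participants who stop treatment but stay.** Sections 7.2 and 8.3.1 read together might suggest that their AE collection stops at an ET visit. The documents as a whole do not support that. Section 7.1 keeps them in the study, the schedules have an AE review at every remaining visit, and SAP 8.2 lists AEs that occur after treatment discontinuation. Only a clarifying phrase is needed.

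**Completers.** The 35 days might be read as a failure to deliver 8 weeks. It needs both visits at opposite ends of their windows, and the mirror case is 77 days. This is ordinary visit tolerance.

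**Effect on the comparison.** A reader might infer that KSI-301 harms will be understated relative to sham. The documents do not show this. The ET rule is the same in both arms, sham eyes are anesthetized, and sham participants can receive open-label KSI-301. The size of any bias is unknown. Moreover, the SAP's frequency tables run through Week 48 and its treatment-emergent window closes at 28 days at the latest, so collecting days 29 to 56 would not change them. Collecting the missing part of the first 28 days could.

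**Pregnancy.** It would be too strong to say that a pregnancy beginning after the last contact would never be reported. Related post-study pregnancy SAEs that the investigator learns of must be. The 90 days is a contraception requirement; the documents do not call it a reporting window.

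**Conclusion.** The point holds for participants who withdraw soon after an injection. Against a stated 56 days, AE and SAE collection can be about 7 days, or 0 if exit is dated at the dosing visit, and this can cut into the SAP's 28-day treatment-emergent window. What need not be reported is a new non-serious event, or a new SAE that the investigator does not hear of or does not judge related.

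The result rests on reading 8.3.1 as written, with ET as the end of collection, and on the absence of any rule tying ET to the last dose. How many participants are affected cannot be derived from the documents. SAP 3.1 and 10.0 report that the sponsor ended development and stopped the study early, which may have sent more participants through ET.

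The pregnancy passages are a secondary matter: the 90-day requirement and the reporting period do not match and should be reconciled. Overall this is a cheap improvement to safety capture and does not undermine the trial's conclusions.

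**What to change.** - **Protocol 8.3.1 and SoA-A footnote 2, with a matching footnote added to SoA-B.** For participants who leave early and have not withdrawn consent to contact, continue AE and SAE collection to the later of the ET visit and 56 days after the last KSI-301 or sham administration, by telephone.
- **Protocol 7.2 and 8.3.1.** State that an ET visit does not end AE collection for participants who stop treatment but remain in the study, in line with 7.1 and SAP 8.2.
- **Protocol 5.1.2, 8.3.5 and 10.6.3.** Reconcile the pregnancy reporting period with the 90-day contraception requirement, for example by asking participants to report a pregnancy conceived within that period.
- **SAP 8.2.** Decide whether the treatment-emergent window should be aligned with 56 days. If it stays at 28, say that events on days 29 to 56 are listed but not tabulated as treatment-emergent.

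If conduct is already over, the clinical study report can instead give post-dose AE observation time by arm for early leavers and state the limitation.

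The cost is protocol wording and a few telephone contacts, with no new visit or procedure. Active capture of pregnancies to 90 days would cost more, because it means a contact about 34 days after Week 100 for each on-time completer of childbearing potential dosed at Week 92. Asking participants to report avoids that.
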